6.1.2. Exclusion Criteria

Potential study patients may not be included in the study if any of the following apply during screening.

- [19] Have received treatment within 28 days or 5 half-lives (whichever is longer) of the initial dose of study drug with an investigational product or nonapproved use of a drug or device (other than the study drug/device used in this study) for noncancer indications or are concurrently enrolled in any other type of medical research judged not to be scientifically or medically compatible with this study.
- [20] For Phase 2 only, more than 1 prior line of therapy for their tumour type.
- [21] Have moderate or severe cardiovascular disease:
- have the presence of cardiac disease, including a myocardial infarction within 6 months prior to study entry, unstable angina pectoris, New York Heart Association Class III/IV congestive heart failure, or uncontrolled hypertension

- have baseline elevated cardiac enzymes as follows: brain natriuretic peptide (BNP) or Cystatin C elevated more than 2xULN or Troponin I elevated above the ULN
- have documented major ECG abnormalities (not responding to medical treatments)
- have major abnormalities documented by ECHO with Doppler:
 - moderate or severe heart valve function defect including moderate or severe valve stenosis or regurgitation
 - left ventricular (LV) ejection fraction <50%, evaluation based on the institutional lower limit of normal
 - have septal aneurysm or other heart aneurysm
 - any aneurysm of the major vessels

For additional details, refer to the attached ECHO guidelines ([Attachment 10](#)).

- [22] Have a serious concomitant systemic disorder including active infection with human immunodeficiency virus (HIV) (HIV 1/2 antibodies).
- [23] Active infection with hepatitis B virus (HBV) (positive hepatitis B surface antigen); HCV is allowed only in HCC patients. HCC patients at risk for HBV reactivation (as defined by anti-hepatitis B core antibody positive) are only eligible in the HCC cohort; see Inclusion Criterion 6.
- [24] Are receiving immunosuppressive agents (eg, cyclosporine) for any reason except for corticosteroids for transfusions. In the Phase 1b portion of the study, low-dose corticosteroids for glioblastoma are permitted (eg, prednisone 10 mg [approximately equivalent to 2 mg of dexamethasone] or less daily or equivalent dose of other corticosteroid).
- [25] Have had prior monoclonal antibody therapy within 28 days before Study Day 1 or not recovered (\leq Grade 1 or at baseline) from AEs (except for fatigue or alopecia) due to agents administered more than 28 days earlier.
- [26] Have had prior therapy with an anti-PD-1, anti-PD-L1, anti-PD-L2, anti-CD137, or anti-cytotoxic T lymphocyte-associated antigen-4 antibody (including ipilimumab or any other antibody or drug specifically targeting T-cell co-stimulation or checkpoint pathways) or a TGF β R1 kinase inhibitor.
- [27] Have a second concurrent primary malignancy that, in the judgement of the investigator and Lilly, may affect the interpretation of results.
- [28] Have prior malignancies. Patients with carcinoma in situ of any origin and patients with prior malignancies who are in remission and whose likelihood of recurrence is very low (such as basal cell carcinoma), as judged by the Lilly clinical research physician (CRP), are eligible for this study. The Lilly CRP will approve enrolment of patients with prior malignancies in remission before these patients are enrolled.

- [29] Receiving any concurrent antineoplastic therapy (ie, chemotherapy, hormonal therapy, immunotherapy, extensive, nonpalliative radiation therapy, or standard or investigational agents).
- [30] Have had prior radiotherapy within 2 weeks of therapy. Patients must have recovered from all radiation-related toxicities, not require more than low-dose corticosteroids (except for low-dose corticosteroids for glioblastoma in the Phase 1b portion of the study, eg, prednisone 10 mg or less daily or equivalent dose of other corticosteroid), and not have had radiation pneumonitis. A 1-week washout is permitted for palliative radiation to non-CNS disease with Lilly physician approval.
- [31] For glioblastoma patients in the Phase 1b portion of the study only, have diffuse leptomeningeal disease.
- [32] Patients with known active central nervous system (CNS) metastases and/or carcinomatous meningitis. Patients with stable, previously treated brain metastases may participate if neurologic symptoms have resolved, they have been off steroids for at least 7 days, and have no evidence of disease progression by imaging for at least 2 weeks before the first dose of study treatment.
- [33] Have active known or suspected autoimmune disease or a documented history of autoimmune disease, or a syndrome that requires systemic steroids or immunosuppressive agents. Patients with vitiligo, alopecia, type I diabetes mellitus, residual hypothyroidism due to autoimmune condition only requiring thyroid replacement therapy (must be on a stable dose started prior to study entry), and/or psoriasis not requiring chronic and systemic immunosuppressive treatment, are permitted to enrol if the above listed conditions are not expected to recur in the absence of an external trigger.
- [34] Patients requiring escalating or chronic supraphysiologic doses of corticosteroids for control of their disease at randomisation are excluded. However, patients with resolved childhood asthma/atopy, who require intermittent use of bronchodilators or local steroid injections, who have hypothyroidism stable on thyroid replacement therapy at study entry, or who have Sjögren's syndrome are eligible for the study.
- [35] Patients with Crohn's disease are not eligible.
- [36] For glioblastoma patients in the Phase 1b portion of the study only, previous treatment with carmustine wafer except when administered as first-line treatment and at least 6 months prior to randomisation.
- [37] Concurrent treatment with Novo-Tumor Treating Fields® (Novocure; Haifa, Israel) is not permitted. Prior whole brain or gamma knife radiosurgery is permitted for the treatment of glioblastoma or metastatic brain lesions.

- [38] Have evidence of interstitial lung disease that is symptomatic or may interfere with the detection or management of suspected drug-related pulmonary toxicity or active, noninfectious pneumonitis.
- [39] Have an active infection requiring systemic therapy.
- [40] Be a pregnant or nursing woman.
- [41] Have received a live vaccine within 30 days before the first dose of study treatment. Examples of live vaccines include, but are not limited to, the following: measles, mumps, rubella, chicken pox, yellow fever, rabies, Bacillus Calmette–Guérin, and typhoid vaccine. Seasonal influenza vaccines for injection are generally killed virus vaccines and are allowed; however, intranasal influenza vaccines (eg, FluMist®) are live attenuated vaccines and are not allowed.
- [42] Have a GI condition that may affect drug absorption.
- [43] Have a history or current evidence of any condition, therapy, or laboratory abnormality that might confound the results of the study, interfere with the patient's participation for the full duration of the study, or is not in the best interest of the patient to participate, in the opinion of the treating investigator.
- [44] Have known psychiatric or substance abuse disorders that in the opinion of the investigator would interfere with cooperation with the requirements of the study.
- [45] Have a history of severe allergy or hypersensitivity to study drug components (including monoclonal antibody therapy).
- [46] For Phase 1b only: Concomitant use of strong CYP3A4 inhibitors and inducers is prohibited. See [Attachment 12](#).
- [47] For HCC patients only:
- have known HCC with fibro-lamellar or mixed histology
 - have presence of clinically relevant ascites
 - have a history of hepatic encephalopathy
 - have had a liver transplant
 - have experienced any Common Terminology Criteria for Adverse Events (CTCAE) Grade 3 or 4 GI bleeding or any variceal bleeding episode in the 3 months prior to enrolment requiring transfusion or endoscopic or operative intervention. (Patients with any bleeding episode considered life-threatening during the 3 months prior to enrolment are excluded, regardless of transfusion or intervention status.)
 - have oesophageal or gastric varices that require immediate intervention (eg, banding, sclerotherapy) or represent a high bleeding risk in the opinion of the investigator or consulting gastroenterologist or hepatologist

6.2. Summary of Study Design

This is a Phase 1b/2 study that will be conducted in 2 parts. The first part (Phase 1b) of the study will consist of an open-label, dose-escalation assessment of the safety and tolerability of galunisertib administered at 50 mg QD (Cohort 1), 50 mg BID (Cohort 2), 80 mg BID (Cohort 3), and 150 mg BID (Cohort 4) administered with nivolumab 3 mg/kg Q2W in patients with advanced refractory solid tumours ([Figure JBEF.6.1](#)). The second part (Phase 2) of the study will be disease restricted to include 2 expansion cohorts in patients with recurrent or refractory NSCLC (n = approximately 25 patients) or HCC (n = approximately 25 patients) receiving nivolumab 3 mg/kg Q2W plus galunisertib at the dose determined from the Phase 1b part. Additional expansion of individual cohorts may occur depending upon activity based upon a 2-stage design after 3 cycles. Details are found in [Section 10.1.1](#). NSCLC has a historically good activity under nivolumab monotherapy; HCC has documented activity with galunisertib therapy.

Additional cohorts of patients with specific alternative tumour histologies may be added, but this addition will require an amendment.

Safety assessments including laboratory assessments, PK blood draws, vital sign collection, medical history, weight and at baseline change in weight for previous 3 months, and physical examinations will be performed according to the schedule of events in [Attachment 1](#). AEs will be assessed continuously during the study and for 100 days after the last dose of combination treatment. ECGs will be collected as described in [Attachment 1](#) and [Attachment 4](#). ECHOs will be collected at baseline and every 8 weeks (end of every other cycle). Additionally imaging examinations will be performed approximately every 8 weeks (end of every other cycle).

Efficacy measures will be assessed following every other treatment cycle (end of Cycles 2, 4, etc). Disease assessment with CT and/or MRI, as appropriate, will be performed at baseline and approximately between Days 22 and 28 of every other cycle and completed before the first dose in the next cycle (or approximately every 8 weeks), until disease progression or patient withdrawal from the study.

Treatment decisions related to patient management and whether to treat a patient with advanced refractory solid tumours with additional cycles of study therapy will be based on RECIST version 1.1 for all study patients except patients with glioblastoma, for whom treatment decisions will be based on RANO criteria.

[figure not shown]
At the sponsor's discretion, scans and measurements may be collected and reviewed by independent radiologists using RECIST version 1.1/RANO criteria at a later date, or at any time during the study.

The planned duration of treatment is not fixed; patients will remain on study treatment until they fulfil 1 of the criteria for study discontinuation ([Section 6.3](#)). Patients demonstrating a benefit from treatment may continue on combination therapy if the patient and investigator feel that the patient is benefiting from treatment. If a patient experiences an AE that requires the patient be discontinued from 1 of the 2 study drugs, the patient should continue on the other study drug

(Section 7.2.4). Landmark analysis of all study patients will occur at 6, 12, and 18 months, and OS will be assessed at the end of trial.

Patients who have discontinued from combination treatment will enter the Safety Follow-Up period with visits at approximately 30 and 100 days. If the patient has only discontinued from 1 of the 2 study drugs, the patient will continue on treatment until they discontinue from the second drug, at which time they will enter the Safety Follow-Up period as noted above. If patients have discontinued treatment for reasons other than disease progression, tumour assessments should continue every 8 weeks until disease progression occurs, initiation of a new anticancer therapy, the patient dies or is lost to follow-up. Patients will be followed for survival approximately every 12 weeks (± 7 days) until death or end of trial. This follow-up may occur through a phone call, email, or visit by the patient or the patient's caretaker.

Refer to [Attachment 1](#) for the study schedule.

Abbreviations: approx = approximately; BID = twice daily; IV = intravenous; HCC = hepatocellular carcinoma; n = number of patients; NSCLC = non-small cell lung cancer; Q2W = every other week; QD = daily; TBD = to be determined.

Figure JBEF.6.1. Study H9H-MC-JBEF design.

6.2.1. Phase 1b Dose Escalation

A 3 + 3 + 3 design will be used to assess the safety of galunisertib given in combination with nivolumab 3 mg/kg. Beginning with Cohort 3 or 4, 1 additional patient will be enrolled in each dose level for a total of 4 patients per dose level to allow for unforeseen discontinuation not due to a DLT before the DLT period is completed (see Section 7.2.2.2). A cycle length for the combination of nivolumab and galunisertib is defined for the purpose of this study to be 28 days. The dosages during dose escalation are provided in Table JBEF.6.1. The DLT observation period will last for 8 weeks or to the completion of Cycle 2, whichever is longer.

After determining the MTD, PAD, or if dose escalation is completed without identifying the MTD and to further explore pharmacodynamic/biomarker objectives, 3 to 12 additional patients may be enrolled in each dose level for a total of up to 15 patients at any dose level.

If at least 50 mg QD of galunisertib cannot be combined safely with nivolumab 3 mg/kg, then following the review of available safety, PK, and pharmacodynamic data at the dose escalation/cohort review meetings, a lower dose of nivolumab may be considered and tested with galunisertib at 50 mg oral QD.

Table JBEF.6.1. Phase 1b Dose Levels

Cohort/Dose Level	Total Number of Evaluable Patients	Galunisertib (PO)	Nivolumab (IV)
1	n=3 to approx 15	50 mg QD 14 days on/14 days off	3 mg/kg Q2W
2	n=3 to approx 15	50 mg BID 14 days on/14 days off	3 mg/kg Q2W
3	n=3 to approx 15	80 mg BID 14 days on/14 days off	3 mg/kg Q2W
4	n=3 to approx 15	150 mg BID 14 days on/14 days off	3 mg/kg Q2W
Total	n=12 to approx 60 total		

Abbreviations: approx = approximately; BID = twice daily; IV = intravenous; PO = orally; Q2W = every 2 weeks; QD = daily.

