6.2.2. Phase 2 Cohort Expansion

The purpose of the cohort expansions is to gather additional safety, PK, tolerability, preliminary efficacy and pharmacodynamic information regarding the combination of galunisertib and nivolumab 3 mg/kg. Once the safety profile of all doses tested has been characterised and the MTD or PAD of combined administration of galunisertib and nivolumab has been defined in the Phase 1b part, the Phase 2 cohort expansions will be initiated at the MTD, or PAD. Treatment doses in the cohort expansion groups will not exceed the MTD. Two expansion cohorts will be tested in order to demonstrate efficacy of the combination in NSCLC and HCC. If DLT-equivalent toxicities occur in 33% or more of patients within a tumour-specific cohort expansion in the first 2 cycles, then investigators and the Lilly CRP will assess the nature and severity of these toxicities. No additional patients will be accrued until this safety review is completed and a decision is made either to continue at the current dose or to deescalate the dose

and define a new dose for the expansion phase. The NSCLC cohort (NSCLC has demonstrated activity with nivolumab monotherapy) and the HCC cohort (HCC has documented monotherapy activity with galunisertib) will be used to assess activity of the combination. Additional cohorts could be considered after reviewing the Phase 1b dose-escalation data to further explore activity of the combination. Any additions would require an amendment.

Approximately 25 patients will be initially enrolled in each cohort. These cohorts may be expanded depending upon activity observed in each individual cohort. These patients will be enrolled to allow for a more precise estimate of the ORR in these tumour types where preliminary data or Phase 3 data have suggested activity for monotherapy. See Section 7.2.3 for dosing information. For all tumour types, patients should receive a minimum of 6 cycles of therapy since responses may take up to 4 to 6 cycles unless they meet 1 of the discontinuation criteria. Patients may continue on combination therapy past 6 cycles if in the opinion of the investigator and the Lilly physician the patient is deriving benefit.

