7.2.2.1. Dose-Limiting Toxicity Determination and Maximum Tolerated Dose Definition

DLT is defined as an AE during Cycles 1 or 2 (8 weeks) that is possibly related to either study drug and fulfils any 1 of the following criteria using the National Cancer Institute's (NCI's) CTCAE version 4.03:

- \geq CTCAE Grade 3 nonhaematologic toxicity. Exceptions that will not be considered a DLT are:
 - nausea, vomiting, diarrhoea, and constipation that can be controlled with treatment
 - fatigue relieved by rest, limiting self-care and/or activities of daily living
 - anorexia not associated with significant weight loss (weight loss of $>10\%$ baseline) or malnutrition (eg, inadequate oral caloric and/or fluid intake); tube feeding or total parenteral nutrition indicated
 - Grade 3 elevations of ALT and/or AST, without evidence of other hepatic injury, in the setting of preexisting hepatic metastasis and baseline elevation of these values may not be considered a DLT if agreed by the study investigator and Lilly CRP
- CTCAE Grade 4 haematological toxicity of >5 days duration
- any febrile neutropenia
- \geq CTCAE Grade 3 thrombocytopenia with clinically significant bleeding
- for nivolumab, any toxicity occurring during Cycles 1 or 2 managed by discontinuation as described in Section 7.2.4.2.
- any other significant toxicity deemed by the primary investigator and Lilly clinical research personnel to be dose limiting (for example, any toxicity that is possibly related to the study medication that requires the withdrawal of the patient from the study during Cycles 1 or 2) or results in the patient getting $<75\%$ of the total doses or leads to holding galunisertib for >2 weeks

Although no inpatient dose escalation or reduction is allowed, for the purposes of patient management, DLTs will lead to dose interruption regardless of the cycle in which a DLT occurs (see Section 7.2.2.2 for specific guidelines).

For the purpose of this study, the MTD is defined as the highest tested dose that has less than 33% probability of causing a DLT.

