A 3 + 3 + 3 design will be used to assess the safety of galunisertib given in combination with nivolumab 3 mg/kg. The dosages during dose escalation are provided in [Table JBEF.6.1](#). The DLT observation period will last for 8 weeks or to the completion of Cycle 2. One additional patient will be enrolled in each dose level for a total of 4 patients per dose level to allow for unforeseen discontinuation not due to a DLT before the DLT period is completed. If at least 3 patients in each dose level complete the DLT period and the fourth patient discontinues for non-DLT reasons prior to completing the DLT period, the dose level will be considered successfully completed. Thus, depending on the number of DLTs observed, the minimum number of evaluable patients will be 3, 6, or 9. For the cohort expansions, up to 4 patients will be enrolled to ensure the minimum number of evaluable patients is achieved (6 or 9 patients).

For the purpose of making decisions on dose escalation from a safety perspective, patients will be considered evaluable if they have received at least 3 of the 4 scheduled nivolumab doses through the 8-week observation period and if at least 75% of the cohort-specified doses of galunisertib were taken (see [Section 7.6.3](#)). Patients who receive fewer than 3 of 4 nivolumab doses or <75% of galunisertib doses for reasons other than AEs or DLTs should be replaced if the minimum number of evaluable patients has not been reached.

- If no DLTs occur in a cohort of 3 or 4 evaluable patients at the lower dose level, a new cohort of 4 patients will be treated at the higher dose level.
- If 1 of 3 or 4 evaluable patients experiences a DLT, up to 4 additional patients (dose level expansion) will be enrolled into the cohort so that a minimum of 6 patients will be evaluable. The dose escalation can proceed if the DLT rate is <33%. If the DLT rate is 33%, up to 4 additional patients (dose level expansion) will be enrolled into the cohort so that a minimum of 9 patients will be evaluable. The dose escalation can proceed if the DLT rate is <33%. If the DLT rate is $\geq 33\%$, then that dose level will be determined to have exceeded the MTD or the intended maximum dose of galunisertib.
- If the DLT rate is >33% (for example, 2 of 3 or 4 evaluable patients experiences a DLT), that dose level will be determined to have exceeded the MTD or the intended maximum dose of galunisertib.

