7.2.3. Phase 2 Cohort Expansion

Once the safety profile of all doses tested has been characterised and the MTD or PAD of combined administration of galunisertib and nivolumab has been defined in the Phase 1b part, the cohort expansions will be initiated.

The Phase 2 part of the study will initially include 2 expansion cohorts (NSCLC and HCC [n = approximately 25 patients per cohort]). Additional cohorts of patients with specific alternative tumour histologies may be added and would require a protocol amendment. If DLT-equivalent toxicities occur in 33% or more of patients within a tumour-specific cohort expansion, then investigators and the Lilly CRP will assess the nature and severity of these toxicities. No additional patients will be accrued until this safety review is completed and a decision is made either to continue at the current dose or to deescalate the dose and define a new dose for the expansion phase. Treatment in all 3 cohorts will consist of 3 mg/kg nivolumab IV on Days 1 and 15 and galunisertib given orally at the dose determined during the Phase 1b part on a schedule of 14 days on/14 days off (taken on Days 1-14). A cycle is 28 days.

Continuous evaluation of toxicity in the cohort expansions will be performed throughout enrolment in the expansion cohorts. If the rate of DLT-equivalent events exceeds 33% in the first 2 cycles, the findings will be discussed and further enrolment may be interrupted. If an expansion cohort is discontinued due to toxicity, a new cohort may be initiated at a previously tested lower dose level.

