10.8. Interim Analyses

Since the Phase 1b part is a dose-finding study, data will be reviewed on a cohort-by-cohort basis during the study, until the MTD (or PAD) is determined. The purpose of these cohort-by-cohort reviews is to evaluate the safety data at each dose level and determine whether a DLT has been observed that would suggest MTD has been met or exceeded. The investigators and the Lilly study team will make the determination regarding dose escalation based upon their review of the safety and tolerability data as described in this protocol.

After all patients who are deemed evaluable for the assessment of dose levels complete a DLT evaluation period or when MTD is determined, an interim safety and PK analysis may be conducted for planning next studies.

For the Phase 2 part, if DLT-equivalent toxicities occur in 33% or more of patients within a tumour-specific cohort expansion, then investigators and the Lilly CRP will assess the nature and severity of these toxicities. No additional patients will be enrolled until this safety review is completed and a decision is made either to continue at the current dose or to deescalate the dose and define a new dose for the expansion phase. The safety review and decision will be documented in writing. Trial-level safety reviews will be conducted approximately 3 months after the first patient begins study drug on Cycle 1 Day 1, approximately 6 months after the first patient begins study drug on Cycle 1 Day 1, and approximately every 6 months thereafter. These evaluations will not be assessed by any formal statistical test; only listings and summaries will be carried out.

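### Phase 1b dose levels may be filled to 15 patients after escalation, but no step requires the DLT rate to be re-checked or enrolment paused as they are treated

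*Protocol*

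**What the plan says.** Protocol 6.2.1 provides that, after the MTD or PAD is determined or escalation finishes without an MTD, and to explore pharmacodynamic and biomarker questions, "3 to 12 additional patients may be enrolled in each dose level for a total of up to 15 patients at any dose level". Table JBEF.6.1 counts 3 to about 15 evaluable patients at each of four levels.

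The DLT rules elsewhere are:

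- **MTD definition (Protocol 7.2.2.1):** "the MTD is defined as the highest tested dose that has less than 33% probability of causing a DLT". No sample size is attached.
- **Escalation (Protocol 7.2.2.2):** decisions are set out for minimum evaluable counts of 3, 6 or 9. At too high a DLT rate, "that dose level will be determined to have exceeded the MTD or the intended maximum dose of galunisertib".
- **Phase 1b review (Protocol 10.8):** "data will be reviewed on a cohort-by-cohort basis during the study, until the MTD (or PAD) is determined".
- **Enrolment pause (Protocol 6.2.2, repeated in 7.2.3, 10.8 and SAP 6.12):** "If DLT-equivalent toxicities occur in 33% or more of patients within a tumour-specific cohort expansion", accrual stops until a safety review is finished and a dose decision made. 10.8 and SAP 6.12 require that decision in writing.
- **Trial-level safety reviews (Protocol 10.8):** at about 3 and 6 months, then every 6 months. "These evaluations will not be assessed by any formal statistical test; only listings and summaries will be carried out".

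**The concern.** The additional patients may start at the point where cohort-by-cohort review is written to stop. They are not in a tumour-specific cohort, so the 33% pause does not count them. A level that passed on as few as 3 evaluable patients can take up to 12 more with no required look at its DLT rate, and those patients can be the majority treated at that level.

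A dose that is too toxic can pass a small escalation cohort by chance, and the extra patients are the first data able to show it. The sponsor already thought a mandatory 33% pause right for Phase 2, at a dose that has cleared escalation. The documents give no reason for treating these Phase 1b patients differently.

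The documents also do not say whether these patients are treated before Phase 2 or alongside it. If before, a rate check would make concrete the Phase 2 entry condition in 7.2.3, which begins "Once the safety profile of all doses tested has been characterised and the MTD or PAD". If alongside, their DLTs do not enter the Phase 2 count.

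**Working it through.** **The plan's own figures.** 3 + 12 = 15 per level; 4 × 3 = 12 and 4 × 15 = 60 in total. Both match Table JBEF.6.1.

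**Which rule reaches which patients.**

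| Rule | Escalation patients | Additional Phase 1b patients | Phase 2 patients |
|---|---|---|---|
| 3+3+3 decisions (7.2.2.2) | Yes | Not stated | No |
| Cohort-by-cohort review (10.8) | Yes | Ends when MTD/PAD is determined | No |
| 33% accrual pause (6.2.2, 7.2.3, 10.8, SAP 6.12) | No | No | Yes |
| MTD definition below 33% (7.2.2.1) | Yes | Can be read to apply; no step checks it | Caps the dose |

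**Size of the gap.** The documents give no true DLT rates, so p = 0.2, 0.3, 0.4 and 0.5 are assumed. Further assumptions: Cohorts 3 and 4 rule, four patients enrolled and evaluable per step, the level then filled to 15, and 33% taken as one third. At 15 patients the threshold is therefore 5 DLTs.

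*Step 1: probability of passing escalation.* The pass paths are 0/4; 1/4 then 0/4 (1/8); and 1/4 then 1/4 (2/8).

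- p = 0.4: 0.6⁴ = 0.1296; (4 × 0.4 × 0.6³) × 0.1296 = 0.3456 × 0.1296 = 0.0448; 0.3456² = 0.1194. Sum 0.294.
- p = 0.5: 0.0625 + 0.0156 + 0.0625 = 0.141.

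*Step 2: one pooled check at 15, given a pass.* From 0/4, 1/8 and 2/8 a flag needs at least 5 of 11, 4 of 7 and 3 of 7 further DLTs.

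- p = 0.4: (0.1296 × 0.467 + 0.0448 × 0.290 + 0.1194 × 0.580) / 0.294 = 0.486.
- p = 0.5: (0.0625 × 0.726 + 0.0156 × 0.500 + 0.0625 × 0.773) / 0.141 = 0.722.

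*Step 3: pause as soon as cumulative DLTs / n reach one third.* Exact recursion from each pass path to n = 15, with outcomes known at once.

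| True DLT rate | Passes escalation | Pooled check flags, given pass | Patient-by-patient pause, given pass |
|---|---|---|---|
| 0.2 | 0.745 | 0.069 | 0.145 |
| 0.3 | 0.508 | 0.242 | 0.352 |
| 0.4 | 0.294 | 0.486 | 0.588 |
| 0.5 | 0.141 | 0.722 | 0.788 |

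Under the Cohorts 1 and 2 rule (pass at 0/3, 1/6 or 2/9) the pooled check flags 0.078, 0.272, 0.538 and 0.777, and the patient-by-patient pause 0.179, 0.404, 0.648 and 0.840.

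*Step 4: DLTs averted by the patient-by-patient pause.* Average room to 15 after a pass is about 8.8 patients, giving 3.51 and 4.39 expected DLTs at p = 0.4 and 0.5. The pause reduces these to 2.40 and 2.42. Multiplied by the chance of passing: (3.51 − 2.40) × 0.294 = 0.33 and (4.39 − 2.42) × 0.141 = 0.28 per level. Checking only every 3 patients averts about 0.15.

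*Step 5: the 8-week DLT window.* With outcomes read 8 weeks after enrolment (accrual rates assumed), the pause comes before the level is full this often:

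| Accrual | p = 0.4 | p = 0.5 |
|---|---|---|
| One patient per 4 weeks | 49% | 68% |
| One patient per 2 weeks | 32% | 46% |
| One patient per week | 7% | 11% |

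The pooled check in Step 2 does not depend on accrual.

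**The case against.** The strongest reply is that the 33% standard already governs these dose levels. The MTD definition has no sample-size limit. The last bullet for Cohorts 3 and 4 in 7.2.2.2 is general, with 2 of 3 or 4 patients given only as an example. Table JBEF.6.1 counts up to about 15 patients as evaluable, which is the term used for dose-level assessment. Other controls remain as well:

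- the sponsor monitors safety throughout (8.1.4);
- 7.3 and 7.6.3 recognise that accrual to a level can be stopped for toxicity;
- 10.8 allows an optional interim safety and PK analysis;
- SAP 6.9.2.1 lists and summarises DLTs by dose level;
- Phase 2 waits for the safety profile to be characterised.

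All of this stands. A reader might infer that these patients are treated without safety oversight, and the documents do not support that.

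The numerical gain can also be over-read. Multiplying pass by not flagged gives 0.294 × (1 − 0.486) = 15.1% and 0.141 × (1 − 0.722) = 3.9%. It is tempting to present this as a fall from 29.4% and 14.1% in toxic doses going forward. That assumes every level is filled, which is optional, and that nobody today would act on 5 DLTs in 15. Neither is supported. Counted before escalation, the pooled check flags a 30% dose 0.508 × 0.242 = 12.3% of the time and a 40% dose 0.294 × 0.486 = 14.3%. It separates the two poorly, because escalation has already removed most toxic doses.

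A reader might also infer that 6.2.1 permits enrolment above the MTD, because "Treatment doses in the cohort expansion groups will not exceed the MTD" appears only under Phase 2. That is strained: 7.2.2.2 already declares such a level to have exceeded the MTD, and nothing in 6.2.1 invites further accrual there.

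What survives is narrow. None of these provisions requires anyone to compute the rate, or to pause, as the additional patients are treated.

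**Conclusion.** The point holds as a cheap improvement in patient safety: the trigger is missing, not the standard or the oversight. As written, up to 12 more patients can be treated at a level that passed on 3, and any pause rests on judgement rather than on the rule the plan uses in Phase 2.

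The expected gain is modest. Averted DLTs are about 0.15 to 0.33 per level at assumed true rates of 40% and 50%, before allowing for the 8-week lag, and fast accrual removes most of the benefit of a running pause. The pooled re-check is the more useful part, flagging about 49% and 72% of passed levels at those rates. These figures assume that the level is filled to 15 and all patients are evaluable. The net benefit is smaller to the extent that sponsor and investigators would have acted without a rule.

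**What to change.** Amend Protocol 6.2.1 and 10.8, and SAP 6.12:

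1. Apply the Phase 2 pause and written review to cumulative DLTs among all evaluable patients at the dose level, including the additional patients, as outcomes become known. Use the version triggered at 33% or more. Protocol 6.2.2 and 7.2.3 also carry a weaker version, under which enrolment may be interrupted if the rate exceeds 33%, so the amendment should say which one applies.
2. Re-check the pooled DLT rate at the selected dose against the below-33% MTD definition before Phase 2 opens or, if it is already open, when the additional patients complete Cycle 2.

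The wording is a few sentences, but it needs a formal protocol amendment and an SAP revision. No new data, reviewers or committee are needed.

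The downside is some reviews at acceptable doses. Given a pass under the Cohorts 3 and 4 rule, the pooled check alone triggers one in about 7% and 24% of levels at true rates of 20% and 30%, and the patient-by-patient pause in about 15% and 35%. Waiting for each 8-week window before enrolling further would add delay. Without waiting, step 1 loses much of its effect under fast accrual and step 2 does not.
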